5.1.1 Adverse events (AE)

According to the code of federal regulation title 21 of the Food and Drug Administration (FDA), an Adverse event refers to any untoward medical occurrence associated with the use of a drug in humans, whether considered drug related or not.

All AEs, whether volunteered, elicited, or noted on physical examination, will be recorded throughout the study (i.e., from signing of the ICF until completion).

All AEs will be collected in and recorded in REDCap.

Classification of an Adverse Event

Severity of event

Each AE will be assigned a category by the Investigator as follows:

Mild: An AE that is easily tolerated by the subject, requires minimal or no treatment and does not interfere with the participant's daily activities.

Moderate: An AE that results in a low level of inconvenience or concern by therapeutic measures. Moderate events may cause some interference with functioning. Intervention may be needed.

Severe: An AE that prevents normal everyday activities and may require systemic drug therapy or other treatment. Severe events are usually potentially life-threatening or incapacitating. If there is a change in severity of an AE, it must be recorded as a separate event.

Relationship of Event

The Investigator will make every effort to assess the relationship of the AE, if any, to the study intervention. The Investigator should use knowledge of the subject, the circumstances surrounding the event, and an evaluation of any potential alternative causes to determine

whether an AE is related to the study treatment. Causality should be assessed using the categories presented below:

Related: The AE is known to occur with the study intervention, there is a reasonable possibility that the study intervention caused the AE, or there is a temporal relationship between the study intervention and event. "Reasonable possibility" means that there is evidence to suggest a causal relationship between the study intervention and the AE.

Not Related: There is no reasonable possibility that the administration of the study intervention caused the event. There is no temporal relationship between the study intervention and event onset, or an alternate etiology has been established.

Action Taken

The investigator will describe the action taken in the appropriate section in REDCap, as follows:

- None
- Study procedure or medication stopped
- Study medication temporarily interrupted
- Concomitant medication
- Other, specify

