The risk to patients from the digital intervention is negligible. The potential benefit of the intervention is improved adherence to opioid agonist/antagonist therapy specifically and medication-assisted therapy in general. This benefit may occur in the patients participating in the trial, and the data collected may extent to future users of the technology.

Medication-assisted therapy is our best hope for combatting the opioid crisis in the near term. Adherence to opioid agonist/antagonist therapy is critical. Pillsy is a technology that can improve adherence to opioid agonist/antagonist therapy and thereby could help curb the current opioid crisis. Since Pillsy is a digital intervention, no physical adverse events are anticipated. However, participants will be undergoing medication-assisted therapy during their clinical care. Patients will be monitored by their respective provider for drug-related adverse events as they would during clinical care. If a provider decides to stop BUP/NAL for any reason (including, but not limited to, a treatment-related adverse event), the participant will also be discontinued from the Pillsy intervention. RCs will attempt to gather subjective feedback about the Pillsy intervention from discontinued participants.

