6.5 Safety Analysis

While we anticipate a very low rate of adverse events, the medical monitor will compare AEs and SAEs between the two arms. We will conduct this analysis to inform the Phase II clinical trial of this intervention.

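### Timing alone is enough to call an adverse event *Related*, and one event can meet both *Related* and *Not Related*, so the causality item recorded for each AE is unreliable

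*Combined protocol and SAP*

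**What the plan says.** Under Relationship of Event in section 5.1.1, the investigator assigns each AE to one of two categories.

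- *Related* has three grounds joined by *or*. The first two are "The AE is known to occur with the study intervention, there is a reasonable possibility that the study intervention caused the AE"; the third is "or there is a temporal relationship between the study intervention and event".
- The next sentence explains the second ground only: a reasonable possibility "means that there is evidence to suggest a causal relationship between the study intervention and the AE". No such condition is attached to the third ground.
- *Not Related* is defined in two sentences: "There is no reasonable possibility that the administration of the study intervention caused the event", then "There is no temporal relationship between the study intervention and event onset, or an alternate etiology has been established".
- The introduction to these definitions asks for "an evaluation of any potential alternative causes to determine" relatedness, and then sends the investigator to the two categories.

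Reporting Adverse Events, in the same section, lists the causal relationship among the items to document for every AE. Section 5.1.3 states "Since Pillsy is a digital intervention, no physical adverse events are anticipated". Section 6.5 says that "the medical monitor will compare AEs and SAEs between the two arms", in order to inform Phase II. Section 5 (Ongoing Assessments) has Pillsy collecting data continuously, and the last assessment is at week 12. Both arms receive a cap; the control arm's is described as inactive and only logs openings.

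**The concern.** A causality scale should separate events that the intervention may have caused from those that merely happened while it was in use. Here the third ground for *Related* removes that separation. The intervention is a device and messaging system in use throughout follow-up, so almost any event after set-up has some temporal relationship to it. Participants in both arms also take BUP/NAL and have opioid use disorder, so events with a cause other than Pillsy are to be expected.

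The second problem is that the two categories are not mutually exclusive. Where both fit, the label depends on which definition the investigator applies, and the documents describe no blinding of the person who assigns it. What is at stake is whether the study can say anything dependable about harm attributed to Pillsy when Phase II is planned.

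**Working it through.** The plan gives no figure to reproduce; this is a check of the definitions.

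**Inputs (all from section 5.1.1).** Four yes/no facts about an AE:
- K: known to occur with the intervention
- R: reasonable possibility of causation, which needs evidence
- T: temporal relationship
- A: alternate etiology established

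This gives 2 × 2 × 2 × 2 = 16 combinations.

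**Step 1: *Related* as written is K or R or T.** It fails only when K, R and T are all *no*, which is 2 combinations (A yes or no). So 16 − 2 = 14 meet *Related*. All 8 combinations with T = yes meet it. In 4 of those 8, R = no; in 2 of those 4, K = no as well, so timing is the only ground.

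**Step 2: *Not Related* as written.** The text does not say how its two sentences combine, so three readings were tried. In none of them does a combination fall in neither category, so the number in both is (number *Related*) + (number *Not Related*) − 16.

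| Reading of *Not Related* | Meets *Not Related* | Meets both |
|---|---|---|
| Strict: R = no, and (T = no or A = yes) | 6 | 14 + 6 − 16 = 4 |
| Middle: (R = no and T = no), or A = yes | 10 | 14 + 10 − 16 = 8 |
| Loose: any one of R = no, T = no, A = yes | 14 | 14 + 14 − 16 = 12 |

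These are counts of logical cases, not expected proportions of events. Under the strict reading, 2 of the 4 overlapping cases have T = yes. The other 2 have K = yes with R = no and T = no, which would be unusual in practice.

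**Step 3: the case that matters.** Take an event in week 5, during use of the system, with no reasonable possibility that Pillsy caused it and another cause established (K = no, R = no, T = yes, A = yes). It is *Related* through "or there is a temporal relationship between the study intervention and event". It is also *Not Related*, through both sentences of that definition. It lies in both categories under all three readings.

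**Step 4: the control arm.** Suppose the same event occurs there. If the inactive cap counts as study intervention, T = yes and the conflict of step 3 recurs. If it does not, T = no, and the event is *Not Related* only. The documents do not settle which applies.

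**Step 5: after the change proposed below.** *Related* is R alone (8 combinations) and *Not Related* is its complement (8). The number in both is 8 + 8 − 16 = 0.

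**The case against.** The strongest reply is that nothing in the plan depends on this label. Section 6.5 compares AEs and SAEs by arm, not related AEs. Section 5.1.2 has SAEs after randomization reported irrespective of relatedness. Under section 5.1.3, leaving the Pillsy intervention follows the provider's stopping of BUP/NAL, not a causality rating. All of this stands. A reader might infer that the between-arm safety comparison is compromised; the documents do not support that.

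A reader might also infer that nearly all events in the Pillsy arm, and almost none in the control arm, would be called related. That contrast assumes that the inactive cap is not study intervention, which the documents leave open, and it takes *temporal relationship* in its broadest sense. If the inactive cap counts, the contrast disappears, although the field would be no more informative.

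Nor does every event with a known other cause fall in both categories. On the strict reading there must also be no reasonable possibility of causation, and the other cause must be established. AEs are recorded from consent, so an event before set-up need not be temporally related; the same holds for one after the intervention is discontinued.

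Finally, the introduction tells the investigator to weigh alternative causes. That is real guidance, but it does not say which category prevails when both are met, and it refers the decision back to the overlapping definitions.

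**Conclusion.** The concern holds as a defect in the definitions. On the plain text, timing alone suffices for *Related*, and at least one realistic type of event (onset during use, no reasonable possibility of causation by Pillsy, another cause established) meets both categories on every reading tried. The causal-relationship item required for each AE is therefore unreliable, and so is any statement about Pillsy-related harm built on it. Identical events may also be labelled differently by arm.

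The conclusion rests on reading *or* in its ordinary sense and on the absence of a stated time window. An investigator who reads *temporal relationship* narrowly would produce fewer conflicts, but the text does not require this. The documents give no AE rates by which to say how many events would be affected. All-cause AE and SAE counts, SAE reporting and the efficacy analysis are untouched.

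**What to change.** In section 5.1.1:

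1. Delete temporal relationship as a stand-alone ground. Define *Related* as a reasonable possibility, supported by evidence, that the Pillsy system caused the event, with timing as supporting evidence only.
2. Define *Not Related* as the complement: every AE that does not meet *Related*.
3. State that *study intervention* means the Pillsy system, and whether that includes the inactive control-arm cap. Section 5.1.1 also speaks of study treatment and study medication; these terms should be reconciled with that definition.

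A separate field for relatedness to BUP/NAL is optional; the overlap is removed without it.

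The cost is a few sentences and a matching instruction for the REDCap causality item, with no change to design, sample size or visits. The downside is that fewer events will be labelled related than under the literal rule: in the enumeration, 8 combinations instead of 14. All AEs would still be recorded and compared by arm.

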5.1.2 Adverse Events or Serious Adverse Events (AEs or SAEs)

An adverse event or suspected adverse reaction is considered "serious" if, in the view of either the investigator or sponsor, it results in any of the following outcomes: Death, a life-threatening adverse event, inpatient hospitalization, prolongation of existing hospitalization, a persistent or significant incapacity/substantial disruption of the ability to conduct normal life functions, or a congenital anomaly/birth defect. Important medical events that may not result in death, though life-threatening or require hospitalization may be considered serious when, based upon appropriate medical judgment, they jeopardize the 's life or require medical or surgical intervention to prevent one of the outcomes listed in this definition. Examples of such medical

events include allergic bronchospasm requiring intensive treatment in an emergency room or at home, blood dyscrasias or convulsions that do not result in inpatient hospitalization, or the development of drug dependency or drug abuse. SAEs are life-threatening adverse events or life-threatening suspected adverse reactions. An adverse event or suspected adverse reaction is considered "life-threatening" if, in the view of either the Investigator or sponsor, its occurrence places the patient at immediate risk of death. It does not include an adverse event or suspected adverse reaction that, had it occurred in a more severe form, might have caused death.

An SAE form must be completed as thoroughly as possible with all available details of the event, signed by the Investigator (or appropriately qualified designee), and emailed to [name] ([contact]), the medical monitor within 24 hours of first becoming aware of the event. Also, SAEs will be reported to [name] at [contact] of Pillsy, Inc and, the Washington State University IRB within 24 hours of first becoming aware of the event.

Reporting of Serious Adverse Events

Any serious adverse event experienced by a participant after randomization will be reported (within 24 hours of the Investigator becoming aware of the event) to Pillsy, Inc and, the Washington State University IRB, whether considered study intervention related or not.

All SAEs will be followed until satisfactory resolution or until the site investigator deems the event to be chronic or the participant is stable. Other supporting documentation of the event may be requested by Pillsy, Inc and should be provided as soon as possible.

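### Section 5.1.2 defines seriousness widely and then limits SAEs to life-threatening events, leaving unclear which events need an SAE form, notice to the medical monitor and a place in the SAE comparison

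*Combined protocol and SAP*

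**What the plan says.** Section 5.1.2 of the combined protocol and SAP opens with a wide definition. An event is serious, in the view of the investigator or the sponsor, if "it results in any of the following outcomes: Death, a life-threatening adverse event, inpatient hospitalization, prolongation of existing hospitalization", or if it results in lasting or significant incapacity or a congenital anomaly. A second sentence adds a further class: "Important medical events that may not result in death, though life-threatening or require hospitalization may be considered serious". The examples given for that class include "blood dyscrasias or convulsions that do not result in inpatient hospitalization".

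The same paragraph then states: "SAEs are life-threatening adverse events or life-threatening suspected adverse reactions". The next sentence explains that an event is life-threatening if "its occurrence places the patient at immediate risk of death", and excludes events that could have been fatal only in a more severe form.

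The paragraph after that requires an SAE form and an email to the medical monitor within 24 hours, and says that SAEs also go to the company and the IRB within 24 hours. Section 6.5 (Safety Analysis) says that "the medical monitor will compare AEs and SAEs between the two arms", to inform the Phase II trial.

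**The concern.** The paragraph answers the question of what an SAE is in two ways, and the answers differ for ordinary cases. A hospital admission that does not put the participant at immediate risk of death is serious under the opening definition and is not an SAE under the later sentence. The acronym that the later sentence defines is the one used for the SAE form, the medical monitor's notice and the SAE comparison. At stake are whether the medical monitor hears of such an event within 24 hours, and whether the SAE counts for the two arms rest on one consistent rule.

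**Working it through.** No sample size, power or event-rate figure is involved. The check sets the statements side by side.

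**Step 1. Count the routes to seriousness.** The opening list has six outcomes, and important medical events make a seventh. The last column applies the later sentence literally.

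| Route | Opening definition | Later sentence |
|---|---|---|
| Death | serious | SAE (taken as within immediate risk of death) |
| Life-threatening event | serious | SAE |
| Hospital admission | serious | only if also life-threatening |
| Prolonged admission | serious | only if also life-threatening |
| Incapacity | serious | only if also life-threatening |
| Congenital anomaly | serious | only if also life-threatening |
| Important medical event | may be serious | only if also life-threatening |

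So 7 − 2 = 5 routes need not count as SAEs under the later sentence.

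**Step 2. Check the important-medical-events clause.** As printed, it describes events that are life-threatening or need hospital care. The opening list already covers those, so the clause would add nothing. Its own example, "convulsions that do not result in inpatient hospitalization", points the other way: the class is meant to reach events outside the list. The negatives appear to have been lost.

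**Step 3. Trace which term each provision uses.**

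- SAE form and 24-hour email to the medical monitor (5.1.2): the acronym.
- 24-hour report to the company and the IRB: stated twice in 5.1.2, once with the acronym and once, under the subheading on reporting of serious adverse events, with the words spelled out. The spelled-out rule covers events after randomization, whether or not related to the intervention, and does not name the medical monitor.
- Seriousness field for each adverse event (Reporting Adverse Events, under 5.1.1): the word *serious*.
- Recording of all adverse events in REDCap, from consent to completion (5.1.1): independent of seriousness.
- Between-arm comparison (6.5): adverse events and, by acronym, SAEs.

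The medical monitor's notice and the SAE half of the comparison therefore rest on the acronym alone. The report to the company and the IRB has a second basis that can be read widely.

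**Step 4. Scale.** The documents give no SAE rate, so no expected count can be derived. Sections 4 and 6.1 plan 15 participants per arm. If one participant's only serious event is classified differently, that arm's SAE proportion changes by 1/15 = 0.067, or 6.7 percentage points.

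**The case against.** The best reply is that this is a drafting slip and that context favours the wide reading. The heading of 5.1.2 treats serious adverse events and SAEs as the same thing. The disputed sentence stands directly before the definition of life-threatening and reads like a misplaced lead-in to it. Taken literally, it would make the six-outcome list and the examples pointless. The important-medical-events clause, although garbled, keeps a working test based on medical judgment and on intervention to prevent a listed outcome. Section 5.1.3 expects no physical adverse events from a digital intervention, and the primary endpoint is untouched.

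Much of that stands as a guess about intent. It does not settle the matter, because nothing in the documents says which statement governs, and a safety-reporting rule should not depend on the reader working out that one of its sentences is misplaced.

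A reader might infer that hospital admissions would go unreported and uncounted. The documents do not support that. All adverse events are recorded and marked serious or not serious, and section 6.5 compares adverse events as well as SAEs, so a misfiled admission would still appear among the adverse events. A reader might also infer that the IRB would not be told within 24 hours. That requires the narrow sentence to override the spelled-out rule as well, which a fair reading need not accept. Nor do the documents leave seriousness to the research coordinator: 5.1.2 gives that judgment to the investigator or sponsor, and the investigator or a qualified designee signs the SAE form.

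**Conclusion.** The contradiction is real and confined to section 5.1.2. Under the literal reading, five of the seven routes to seriousness need not count as SAEs. Those events could miss the SAE form and the 24-hour notice to the medical monitor, and could drop out of the SAE comparison in section 6.5. The seriousness flag does not resolve this, since whoever fills it in needs one definition and the section supplies two.

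The consequence is limited to classification as an SAE and what follows from it. The adverse-event record survives, and reporting to the company and the IRB after randomization has a separate basis. The count of five assumes that a fatal event falls within the life-threatening category and that the later sentence is applied as written. How many participants would be affected is unknown. The primary adherence analysis is not affected. The wording should be corrected because it governs safety reporting and the repair is small.

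**What to change.** Reconcile section 5.1.2 so that one definition governs the seriousness field, the 24-hour reports and the SAE comparison in section 6.5:

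1. Delete the sentence "SAEs are life-threatening adverse events or life-threatening suspected adverse reactions". Keep the definition of life-threatening that follows it, which the opening list needs.
2. Reword the important-medical-events clause to agree with its own examples: such events may be judged serious even when they do not cause death, are not life-threatening and do not need hospital admission.

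The cost is two sentences of protocol wording. No visits, data items, participants or changes to the efficacy analysis are needed.

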5.1.3 Other Safety Considerations

Data and Safety Monitoring Plan

Patients receiving opioid use disorder treatment will receive care as usual. Half of the participants will also receive the Pillsy intervention. The Pillsy intervention is a smart pill cap, mobile application with text and other messaging capability. We will keep enrollment to the lowest numbers possible that still allow sufficient power to answer research questions.

The risk to patients from the digital intervention is negligible. All data is collected in a HIPAA-compliant manner. Private identifiable information will be encrypted and kept secure.

Study visits will be conducted in a manner to protect participant privacy. The consent process, administration of questionnaires, etc. will occur in a private area. To reduce the risk of unauthorized disclosure of confidential information all personal identifiers will be kept separate from participant files and a study specific research identification number (key) will be assigned to each participant. Data will be collected, entered and accessed by study personnel trained in issues of confidentiality related to human subject protection. The key will be kept separate and not in the same enclave component of the network. Data will be entered into a password-protected database that is encrypted and firewalled. The consent form states that all information provided by the participant will be kept private except in the case that this would immediately put the participant or someone else in danger. In that case the Investigator would release information to keep the participant or another person safe. The consent states that if

Investigator learn about abuse to a child or an elder, that information must be reported to the proper authorities.

As in all research of this nature, there is the possibility of discomfort or embarrassment related to questions dealing with opioid use and social stigma for engaging in these types of behaviors. Participants will be informed that they have the right to refuse to answer any question. If participants find any aspects of their involvement in the research study particularly distressing, they will be encouraged to discontinue participation.

The risk to patients from the digital intervention is negligible. The potential benefit of the intervention is improved adherence to opioid agonist/antagonist therapy specifically and medication-assisted therapy in general. This benefit may occur in the patients participating in the trial, and the data collected may extent to future users of the technology.

Medication-assisted therapy is our best hope for combatting the opioid crisis in the near term. Adherence to opioid agonist/antagonist therapy is critical. Pillsy is a technology that can improve adherence to opioid agonist/antagonist therapy and thereby could help curb the current opioid crisis. Since Pillsy is a digital intervention, no physical adverse events are anticipated. However, participants will be undergoing medication-assisted therapy during their clinical care. Patients will be monitored by their respective provider for drug-related adverse events as they would during clinical care. If a provider decides to stop BUP/NAL for any reason (including, but not limited to, a treatment-related adverse event), the participant will also be discontinued from the Pillsy intervention. RCs will attempt to gather subjective feedback about the Pillsy intervention from discontinued participants.

